7.1.5 Pregnancies and Contraception Requirements

For the purposes of this study, a female of childbearing potential is defined as any female who has experienced menarche and is pre-menopausal; a postmenopausal state is defined as no menses for 12 months without an alternative medical cause in a previously menstruating female.

For the purposes of this study, acceptable contraception is defined below based on *Nonclinical Safety Studies for the Conduct of Human Clinical Trials and Marketing Authorization for Pharmaceuticals: ICH M3(R2)* dated January 2010, and other available guidelines ([“U.S. Medical Eligibility Criteria for Contraceptive Use, 2010” 2010](#); [“Recommendations related to contraception and pregnancy testing in clinical trials” 2014](#); [“M3\(R2\) Nonclinical Safety Studies for the Conduct of Human Clinical Trials and Marketing Authorization for Pharmaceuticals” 2010](#)):

- a) All female subjects of childbearing potential must use highly effective contraception, which includes the use of one or more of the following acceptable methods:
 - i. Surgical sterilization (e.g., bilateral tubal occlusion or ligation, hysterectomy, bilateral salpingectomy, bilateral oophorectomy)
 - ii. Total (as opposed to periodic or cyclic) abstinence
 - iii. Hormonal contraception associated with consistent inhibition of ovulation; these may include (but are not necessarily limited to) oral, intravaginal, implantable, injectable, or transdermal delivery methods.
 - i. Progesterone only oral contraceptives are excluded as a highly effective method, as they do not consistently inhibit ovulation.
 - iv. Intrauterine device/system

- v. Exclusive monogamous heterosexual intercourse with a sterilized (i.e., vasectomized) or otherwise non-fertile (e.g., castrated) male partner

Any pregnancy occurring in a female subject or the female partner of a male subject, from the first study drug administration through the 4-week follow-up visit must be reported within 24 hours of the investigator's awareness of the pregnancy. See SAE and Pregnancy Form Report Completion Guidelines for complete instructions.

The investigator will follow the pregnancy to delivery or other pregnancy outcome.

Pregnancy in a female clinical trial subject or female partner of a male clinical trial subject is not an SAE per se. Complications of such pregnancies (for example, spontaneous abortion) may qualify as SAEs and should be reported as such even if they occur after the Follow-up visit. Any congenital anomalies/birth defects must be recorded and reported as SAEs. See SAE and Pregnancy Form Report Completion Guidelines for complete instructions.

7.2 Methods and Timing for Recording and Reporting Adverse Events

7.2.1 Adverse Event Reporting Period

Any AE occurrence during the study must be recorded on source documentation and eCRF at the site, in accordance with protocol instructions.

AEs and SAEs will be recorded from the first study drug administration through the follow-up visit. After the 4-week follow-up visit, only SAEs that are believed to be drug-related should be reported.

After informed consent but prior to initiation of study drug, only SAEs considered by the investigator to be caused by a protocol-mandated intervention will be collected (e.g. SAEs related to invasive procedures such as blood collection). These procedure-related SAEs should only be reported on the SAE form, not on the AE form of the eCRF. Subjects who undergo screening procedures but are not randomized into the study will not have SAEs recorded in the clinical database.

7.2.2 Eliciting Adverse Events

Investigators will seek information on AEs and SAEs at each subject contact through the follow-up visit. All AEs and SAEs, whether reported by the subject or noted by authorized study personnel, will be recorded in the subject's medical record and on the AE eCRF page, and, if serious, on the SAE form. For each AE and SAE recorded, the investigator will make an assessment of seriousness, severity, and causality.

7.2.3 Assessment of Severity

All AEs entered into the eCRF will be graded for severity using the National Cancer Institute Common Terminology Criteria for Adverse Events (NCI CTCAE) v4.03

(“Common Terminology Criteria for Adverse Events (CTCAE)” 2010) to describe the maximum intensity of the AE.

If the AE cannot be found in the event-specific NCI CTCAE grading criteria, the investigator should use the definitions for Grade 1, 2, 3, and 4 in [Table 1](#).

Table 1 Adverse Event Grading

Grade	Severity	Alternate Description^a
1	Mild (apply event-specific NCI CTCAE grading criteria)	Asymptomatic or mild symptoms; clinical or diagnostic observations only; intervention not indicated.
2	Moderate (apply event-specific NCI CTCAE grading criteria)	Minimal, local or noninvasive intervention indicated; limiting age-appropriate instrumentation activities of daily living (ADL) ^b
3	Severe (apply event-specific NCI CTCAE grading criteria)	Severe or medically significant but not immediately life-threatening; hospitalization or prolongation of hospitalization indicated; disabling; limiting self care ADL ^c
4	Very severe, life threatening, or disabling (apply event-specific NCI CTCAE grading criteria)	Life-threatening consequences; urgent intervention indicated.
5	Death related to AE	

^aUse these alternative definitions for Grade 1, 2, 3, and 4 events when the observed or reported AE is not in the NCI CTCAE listing. A semi-colon indicates ‘or’ within the alternate description of the grade.

^bInstrumental ADL refer to preparing meals, shopping for groceries or clothes, using the telephone, managing money, etc.

^cSelf care ADL refer to bathing, dressing and undressing, feeding self, using the toilet, taking medications, and not bedridden.

Source: National Cancer Institute Common Terminology Criteria for Adverse Events (NCI CTCAE) v4.03 (“Common Terminology Criteria for Adverse Events (CTCAE)” 2010)

Note that severity, a measure of intensity, is not equivalent to seriousness, a regulatory definition of outcome. Regardless of severity, some AEs may meet the criteria for seriousness. See [Section 7.1.2](#) for the definition of an SAE.

If an adverse event changes in severity during the same study period (e.g., treatment period), only the highest severity grade will be recorded on the eCRF.

7.2.4 Assessment of Causality

The investigator’s assessment of causality must be provided for all AEs (serious and non-serious). An investigator’s causality assessment is the determination of whether there exists a reasonable possibility that the investigational product caused or contributed to an AE. Causality of an AE will be assessed by the investigator using the following terms:

- **Likely Related:** A reaction that follows a reasonable temporal sequence from administration of the study drug; that follows a known or expected response pattern to the suspected study drug; and for which other potential etiologies are considered less likely factors than the study drug.
- **Likely Unrelated:** A reaction that, considering all potential etiologies, is most likely due to factors other than the study drug.

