1.3.3 Serlopitant in Pruritus-Related Studies

Serlopitant has been evaluated in two completed Phase 2 studies of subjects with chronic pruritus (TCP-101 and TCP-102). In TCP-101, a Phase 2 study of 256 adult subjects 18 to 65 years of age with chronic pruritus), treatment-emergent AEs (TEAEs) were reported for 25.4% of subjects in the placebo group and 32.8%, 36.9%, and 37.5% of subjects in the serlopitant 0.25, 1, and 5 mg groups, respectively. Overall, headache was the most commonly reported TEAE, reported for 6.3% of subjects in the placebo group and 1.6%, 4.6%, and 1.6% of subjects in the serlopitant 0.25, 1, and 5 mg groups, respectively. Somnolence and diarrhea were the TEAEs with the highest overall incidence in the serlopitant groups. Most TEAEs were mild or moderate in severity. Six subjects discontinued study drug due to a TEAE; the events considered treatment-related in the serlopitant groups were diarrhea and gastrointestinal (GI) pain. There was no evidence of meaningful trends in laboratory abnormalities or changes in vital signs.

In TCP-102, a Phase 2 study of 127 adult subjects 18 to 80 years of age with PN, TEAEs were reported for 61.9% of subjects in the placebo group and 71.9% of subjects in the serlopitant 5 mg group. The most common TEAEs in the serlopitant group were nasopharyngitis (17.2% serlopitant, 3.2% placebo), diarrhea (10.9% serlopitant, 4.8% placebo), and fatigue (9.4% serlopitant, 6.3% placebo). Most TEAEs were mild or moderate in severity. Five subjects (3 serlopitant, 2 placebo) had serious adverse events (SAEs); those considered possibly related to study drug in the serlopitant group were depression, dizziness, and vertigo. Nine subjects discontinued study drug due to a TEAE; those considered treatment-related in the serlopitant groups were pruritus, neurodermatitis, headache, dizziness, and vertigo. No clinically relevant changes were observed in chemistry, hematology, vital signs, or electrocardiogram (ECG) results.

Additional studies are currently ongoing in pruritus associated with atopic dermatitis and epidermolysis bullosa.

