5.6 Study Drug Discontinuation

Subjects will be discontinued from study drug treatment in the following events:

- A female subject becomes pregnant
- Subject decision to discontinue study drug treatment, or subject decision to withdraw consent from the study
- The subject receives a strong CYP3A4 inhibitor
- Any medical condition that may jeopardize the subject's safety if study drug is continued, in the investigator's and/or Sponsor's opinion
- Discontinuation is deemed to be in the best interest of the subject, in the investigator's and/or Sponsor's opinion
- The subject experiences a NCI CTCAE Grade 2 or higher treatment emergent AE that is assessed as likely related to study drug

The Sponsor or designee should be contacted within 24 hours of investigator's awareness of any study drug treatment discontinuation. Investigators should make every effort to contact the Sponsor or designee before discontinuing study drug treatment, if possible.

Subjects who discontinue treatment with study drug prior to completing the treatment period will have a Follow-up visit 28 days after their last dose of study drug (see [Section 6.5.11](#)). Every effort should be made for subjects to complete the Follow-up visit after a subject has discontinued from study drug.

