7.3 Follow-up of Adverse Events and Serious Adverse Events

The investigator must make every effort to follow all AEs and SAEs regardless of attribution until judged resolved or stabilized, the subject is lost to follow-up, or it has been determined that study drug treatment or participation in the study is not the cause of the AE or SAE.

7.4 Reporting Serious Adverse Events to the Sponsor and Institutional Review Board or Ethics Committee

The Sponsor or designee is under obligation to report certain SAEs to regulatory authorities related to investigational drugs in clinical trials. The Sponsor or designee must be notified within 24 hours of an AE when the investigator determines that an AE meets the protocol definition of an SAE, regardless of the cause or relationship to study drug.

An SAE related to study participation occurring before study drug administration and after informed consent should be promptly reported to the Sponsor. If the investigator learns of any SAE at any time after a participant has been discharged from the study, and the SAE is considered likely related to study drug, the SAE should be promptly reported to the Sponsor.

Please see the SAE and Pregnancy Form Report Completion Guidelines for safety reporting instructions.

The investigator must also comply with applicable requirements concerning reporting of SAEs to the Institutional Review Board (IRB) or Ethics Committee (EC). This may include initial or follow-up notification of an SAE or other safety information.

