7.5 Reporting Serious Adverse Events to Regulatory Authorities and Study Investigators

The Sponsor, or its designee, is responsible for submitting reports of serious, unexpected related AEs to regulatory authorities on an expedited basis, according to the ICH E2A Guideline and to other regulatory authorities according to national and local regulations as required. The Sponsor, or its designee, is responsible for prompt submission to the IRB or EC of any expedited SAE reports submitted to regulatory authorities. All investigators participating in ongoing clinical studies with serlopitant will receive copies of the SAE reports submitted on an expedited basis to regulatory authorities.

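### The Likely Related definition in Protocol 7.2.4 demands an already known or expected reaction pattern, so a new type of drug-caused reaction fits neither permitted causality term

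*Protocol*

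**What the plan says.** Protocol 7.2.4 requires the investigator to rate causality for every AE, serious or not. Its lead sentence describes the judgement as "whether there exists a reasonable possibility that the investigational product caused or contributed to an AE". It then names two terms to be used.

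- *Likely Related* has three conditions: a reasonable time sequence, and a reaction "that follows a known or expected response pattern to the suspected study drug; and for which other potential etiologies are considered less likely factors" in comparison with serlopitant.
- *Likely Unrelated* is "A reaction that, considering all potential etiologies, is most likely due to factors other than the study drug".

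There is no third term.

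Relatedness is then used in several places. Protocol 5.6 lists among its discontinuation criteria: "The subject experiences a NCI CTCAE Grade 2 or higher treatment emergent AE that is assessed as likely related to study drug". Protocol 7.4 asks for prompt reporting of an SAE learned of after discharge if it is considered likely related, while 7.2.1 limits late SAE reports to those believed to be drug-related. In 7.5 the sponsor "is responsible for submitting reports of serious, unexpected related AEs to regulatory authorities on an expedited basis". Protocol 8.10.1 tabulates treatment-related AEs, and SAP 9.7.1 adds study-drug-related SAEs.

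**The concern.** The lead sentence asks whether the drug may have caused or contributed to the event. It says nothing about whether the reaction has been seen before. The *Likely Related* term adds that requirement and joins it to the other two with an 'and', so failing it is enough to rule the term out. A reaction not previously associated with serlopitant is then the one event that cannot be called related, however strong the other evidence.

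This matters because Protocol 3.2 states that serlopitant has not been studied in refractory chronic cough, and the only ongoing safety review described (3.4.1) is internal and blinded. Two sites facing the same new reaction could rate it differently, one following the lead sentence and the other the definition. At stake are the related-AE and related-SAE counts, the rule for SAEs found after discharge, one discontinuation criterion, and possibly the classification behind expedited reports.

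**Working it through.** No arithmetic applies: the plan states no figure on this point, and the definition uses none. The check is to apply the 7.2.4 terms to each kind of event and then follow the rating to each rule that uses it.

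**Step 1: do the two terms cover every event?** Assume the timing is plausible.

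| Pattern | Most likely cause | Likely Related? | Likely Unrelated? |
|---|---|---|---|
| Known or expected | Drug | Yes | No |
| Known or expected | Drug and another cause equally likely | No (third condition fails) | No |
| Known or expected | Another cause | No | Yes |
| New | Drug | No (second condition fails) | No |
| New | Drug and another cause equally likely | No (second and third fail) | No |
| New | Another cause | No | Yes |

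Three of the six rows have no permitted rating. The fourth is the important one: the drug is the leading explanation, the lead sentence is plainly met, and neither term applies. Because a rating is compulsory, the site must stretch one definition or the other.

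**Step 2: where does the rating lead?**

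| Place | What it uses | Effect of the definition |
|---|---|---|
| Protocol 8.10.1; SAP 9.7.1 | Treatment-related AEs; drug-related AEs and SAEs | Under-count if a new reaction is forced into *Likely Unrelated* |
| Protocol 7.4, SAEs after discharge | Likely related | Affected directly; 7.2.1 uses different, broader wording |
| Protocol 5.6, Grade 2 or higher criterion | Likely related | Affected directly; criteria on jeopardy to safety and on the subject's best interest need no rating |
| Protocol 7.5, expedited reports | Serious, unexpected and related | At risk if the sponsor takes over the site's term |
| Protocol 7.4, in-study SAEs | 24-hour notice to the sponsor whatever the relationship | Not affected |
| Protocol 7.3, follow-up | All AEs and SAEs, whatever the attribution | Not affected as written |
| Protocol 8.10.1; SAP 9.7.1, all AEs and all SAEs by arm | No causality filter | Not affected |

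**Step 3: does 7.5 fit 7.2.4?** Expedited reports concern "submitting reports of serious, unexpected related AEs to regulatory authorities on an expedited basis". If related there means *Likely Related*, an event has to follow an expected pattern before it can be reported as unexpected. The protocol describes no separate sponsor causality assessment that would settle this. It does not bind the sponsor to the site's term either.

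**The case against.** The best defence is that an experienced investigator will follow the lead sentence, and that an expected pattern can be taken to include class or pharmacological effects. That may well happen. But the text refers to the response pattern of the suspected study drug and does not say which reading governs, so the inconsistency stays.

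The defence is stronger on consequences. A reader might infer more than the documents support in four respects.

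- **That new reactions escape expedited reporting.** Every in-study SAE goes to the sponsor within 24 hours, and the expedited decision is the sponsor's under 7.5. The documents also do not say that expected in 7.2.4 and unexpected in 7.5 rest on one concept.
- **That such events lose follow-up.** Section 7.3 covers all events whatever the attribution. It ends follow-up on causal grounds only when "it has been determined that study drug treatment or participation in the study is not the cause of the AE or SAE". A rating that other factors are most likely is not that determination.
- **That the problem can be sized from the earlier prurigo nodularis study.** Its percentages imply arms of 64 and 63 (46/64 = 71.9%, 39/63 = 61.9%), and 3 serlopitant subjects had SAEs. Scaling gives 3/64 × 85 = 4.0 subjects here. That is a count of subjects with SAEs, not of misclassified events, and treatment there lasted 8 weeks rather than 12.
- **That related counts cannot be compared with earlier studies.** Protocol 1.3.3 reports SAEs in which "those considered possibly related to study drug in the serlopitant group were depression, dizziness, and vertigo". It gives no causality definitions for those studies. These events are also already documented with serlopitant, so they do not illustrate a new reaction.

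It is also fair to say that a new toxicity can show in the comparison of all AEs and SAEs by arm, which needs no relatedness rating.

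**Conclusion.** The definition is defective. *Likely Related* excludes a new type of reaction by its wording, the two terms are not exhaustive, and both depart from the standard stated at the head of the same section. The consequences are limited. The related-AE and related-SAE tables can be under-counted, and the post-discharge SAE rule in 7.4 and one criterion in 5.6 rest on an unsound term. Expedited reporting carries a risk that depends on whether the sponsor relies on the site's rating. In-study SAE notification, follow-up under 7.3 and the unfiltered AE and SAE tables are untouched.

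The number of events affected cannot be estimated from the documents. The direction, fewer events rated related, assumes that sites apply the definition as written and resolve an unclassifiable event as *Likely Unrelated*. The effect on the tables also assumes that they use the investigator's term, since neither document defines related for the analysis.

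**What to change.** In Protocol 7.2.4, remove the known or expected pattern as a required condition and keep it as supporting evidence. Reword the two terms so that together they cover every event, ties included, and agree with the reasonable-possibility sentence. How much weight competing causes should carry is a threshold choice; the sponsor should make it openly and state it.

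Use the same causality term in 7.2.1, 7.4 and 7.5, and define related in 8.10.1 and SAP 9.7.1 by that term. State in 7.5 whether the sponsor makes its own causality assessment. Section 5.6 must be reconciled with the revised definition by saying which causality standard it refers to; what that clinical rule should be is not proposed here.

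The cost is protocol and SAP wording plus eCRF guidance. Somewhat more events will be rated related, and there may be a few more expedited reports.

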7.3 Follow-up of Adverse Events and Serious Adverse Events

The investigator must make every effort to follow all AEs and SAEs regardless of attribution until judged resolved or stabilized, the subject is lost to follow-up, or it has been determined that study drug treatment or participation in the study is not the cause of the AE or SAE.

7.4 Reporting Serious Adverse Events to the Sponsor and Institutional Review Board or Ethics Committee

The Sponsor or designee is under obligation to report certain SAEs to regulatory authorities related to investigational drugs in clinical trials. The Sponsor or designee must be notified within 24 hours of an AE when the investigator determines that an AE meets the protocol definition of an SAE, regardless of the cause or relationship to study drug.

An SAE related to study participation occurring before study drug administration and after informed consent should be promptly reported to the Sponsor. If the investigator learns of any SAE at any time after a participant has been discharged from the study, and the SAE is considered likely related to study drug, the SAE should be promptly reported to the Sponsor.

Please see the SAE and Pregnancy Form Report Completion Guidelines for safety reporting instructions.

The investigator must also comply with applicable requirements concerning reporting of SAEs to the Institutional Review Board (IRB) or Ethics Committee (EC). This may include initial or follow-up notification of an SAE or other safety information.

7.5 Reporting Serious Adverse Events to Regulatory Authorities and Study Investigators

The Sponsor, or its designee, is responsible for submitting reports of serious, unexpected related AEs to regulatory authorities on an expedited basis, according to the ICH E2A Guideline and to other regulatory authorities according to national and local regulations as required. The Sponsor, or its designee, is responsible for prompt submission to the IRB or EC of any expedited SAE reports submitted to regulatory authorities. All investigators participating in ongoing clinical studies with serlopitant will receive copies of the SAE reports submitted on an expedited basis to regulatory authorities.

7.6 Emergency Unblinding

Emergency unblinding is available 24 hours per day/7 days per week and will be performed via IWRS. An Investigator may unblind a subject's treatment assignment only when knowledge of the investigational product is essential for the welfare of a subject. There is no specific antidote for serlopitant and usual supportive medical management is recommended in the case of a medical emergency.

